6.2.3.3. ANCOVA Analysis

The ANCOVA analysis defined in Section [6.2.2](#) will be repeated as a sensitivity analysis using the actual stratification factors in the model.

6.2.4. Subgroup Analyses

The ANCOVA method will also be applied to the following subgroups for the change from baseline values in the number of migraine days and the monthly average number of headache days of at least moderate severity.

- participants receiving or not receiving any concomitant preventive treatment at baseline
- participants in different race groups (caucasian, non-caucasian)
- participants by age group (6-11 years, 12-17 years)
- participants by weight group
- participants by puberty status
- participants by sex
- participants by region

The model to be used in exploring the consistency of a treatment effect (ie, TEV-48125 – placebo) across the subgroup levels will have treatment, subgroup, and treatment-by-subgroup interaction as fixed effects, and a baseline covariate that corresponds to the respective endpoint (ie, response variable in the model). For ease of modeling purposes, a comparable cell means

parameterization will be used. Hence when assessing the treatment effect for change from baseline in number of migraine days in the age subgroup, the model will have treatment, age, and treatment-by-age interaction as fixed effects, and baseline number of migraine days as a covariate. Likewise, when assessing the treatment effect for change from baseline in number of migraine days in the weight subgroup, the model will have treatment, weight, and treatment-by weight interaction as fixed effects, and baseline number of migraine days as a covariate. For the by month analyses, MMRM will be performed in a similar manner in which the within subject covariance structure is the same as in Section 6.2.3.1. Actual rather than ‘as randomized’ stratification values will be used.

The estimated treatment effects at each subgroup level will be based on the least squares means treatment difference at each subgroup level and their corresponding two-sided 95% confidence intervals obtained from each of the respective models. Since there is a continuous covariate in each of these subgroup analyses, the least squares means will need to be adjusted to a common overall baseline value.

The results from the subgroup analysis will be displayed graphically using a forest plot.

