2.2. Randomization and Blinding

This is a double-blind trial. The Sponsor, Investigators, trial staff (except for staff involved in bioanalytical analyses), and participants will be blinded to treatment assignment. A computer-generated master randomization list will be provided to drug packaging facilities. Packaging vendor(s) will package active and placebo into single-visit kits according to Good Manufacturing Practice procedures. The active drug and placebo kits for each dose will be identical in appearance and will contain 1 pre-filled syringe (PFS) (for the 225 mg dose and its matching placebo) or 2 vials (for the 120 mg dose and its matching placebo). Adequate kit supply for upcoming trial visits will be managed by interactive response technology (IRT) and kept (refrigerated at 2°C to 8°C) on site.

This is a randomized trial. Randomization will be stratified by country, sex, puberty status, and preventive medication use at baseline (Yes/No). Participants will be randomly assigned to treatment groups by means of a computer-generated randomization list. The specifications for randomization will be under the responsibility and oversight of Teva Global Statistics. Each participant will undergo randomization in a 1:1 ratio within the stratum to which he or she belongs to receive test IMP or placebo IMP, as assigned by the IRT. The IRT will manage initial drug supply, maintenance of adequate IMP supplies on site, and trial randomization centrally. At the time of each trial visit, the IRT will be queried, and site personnel will retrieve and administer a 1.5 mL volume for participants weighing ≥ 45.0 kg at randomization (visit 2) or a 0.8 mL volume for participants weighing <45.0 kg at randomization (visit 2) from each PFS or 2 vials contained in the appropriately numbered kit(s).

The Sponsor's clinical personnel (and delegates) involved in the trial will be blinded to the identity of the IMPs until the database is locked for analysis and the IMP assignment is known. However, if a prioritized sample analysis is needed, bioanalytical and clinical pharmacology personnel may be unblinded.

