6.2.2. Primary Analysis of the Primary Estimand

The hypothesis testing for the primary analysis is

$$H_o : \delta_1 = \delta_2 \quad vs \quad H_a : \delta_1 \neq \delta_2$$

where δ_1 and δ_2 are the parameters of mean change from baseline in the monthly average number of migraine days for the TEV-48125 treatment group and the placebo group respectively. The estimated difference of TEV-48125 dose vs. placebo will be tested following the pre-specified fixed sequence as specified in [Section 7](#).

An analysis of covariance (ANCOVA) method will be applied for the primary analysis. The model will include treatment, sex, puberty status, region (United States or Other ([Table 1](#))), weight category ($<45.0\text{kg}$ or $\geq 45\text{ kg}$) and baseline preventive migraine medication use (yes/no) as fixed effects and the baseline number of migraine days as a covariate. The stratification factors (as randomized) will be used in the model. The least squares (LS) means for the treatment groups, LS means and corresponding 95% confidence intervals for the treatment differences (TEV-48125 – placebo), and associated p-value will be provided.

A hierarchical procedure will be used to control Type 1 error rate, as described in [Section 7](#).

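### The SAP 6.2.4 subgroup models omit four or five of the primary model's categorical factors without a stated reason, and headache days by age get two different models

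*SAP*

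**What the plan says.** In SAP 6.2.2, "The model will include treatment, sex, puberty status, region" and also weight category and "baseline preventive migraine medication use (yes/no) as fixed effects and the baseline number of migraine days as a covariate". The same five categorical factors appear in the MMRM (6.2.3.1), the multiple-imputation analysis (6.2.3.2), the repeat ANCOVA with actual strata (6.2.3.3) and the secondary ANCOVAs (6.3.2).

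SAP 6.2.4 covers seven subgroupings (preventive use, race, age, weight, puberty status, sex, region) for two endpoints: migraine days and headache days of at least moderate severity. Its model "will have treatment, subgroup, and treatment-by-subgroup interaction as fixed effects", together with "a baseline covariate that corresponds to the respective endpoint". Worked examples for age and weight add no further term. For weight, "the model will have treatment, weight, and treatment-by weight interaction as fixed effects", which also shows that the subgroup factor stays in its own model. Actual strata values are used, and the by-month MMRM is built in the same way.

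The stated purpose is modest: "The model to be used in exploring the consistency of a treatment effect" across subgroup levels. The results go into a forest plot.

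**The concern.** The primary model treats the five factors as worth adjusting for. The SAP amendment log says that weight group was added to the primary model and the MMRM so that its effects could be controlled. Section 6.2.4 leaves most of these factors out and gives no reason; its remark about ease of modelling concerns only the cell-means parameterisation.

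Weight determines dose, and neither age nor weight category is a randomisation stratum, so how consistent the effect is across those groups is a natural question for a paediatric product. At stake is how steady the forest-plot points are, and whether the report carries one answer or two for the same endpoint and age group.

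**Working it through.** **1. The plan's own figure.** Inputs (SAP 2.4 and 7): difference 1.7 days, SD 4.92, 133 per arm, two-sided alpha 0.05. SE = 4.92 × √(2/133) = 0.603; 1.7/0.603 = 2.82; power = Φ(2.82 − 1.96) = 80.4% (80.2% by noncentral t). 266/0.96 = 277.1, so 278 randomised. The stated figures reproduce. The documents give no figure for subgroup precision, so 4.92 is used below only to set the scale.

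**2. Terms side by side.**

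| Subgroup model | Primary factors kept | Primary factors absent |
|---|---|---|
| Age, race | none | all five |
| Sex, puberty status, region, weight, preventive use | the subgroup factor itself | the other four |

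The endpoint's own baseline stays in every model.

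**3. Cost of restoring them.** Each model is fitted once to the whole FAS, so the factors enter as common main effects. With 266 participants, the short model has 5 parameters and 261 residual degrees of freedom. Adding four or five two-level factors leaves 257 or 256. (Puberty status is assumed to have two levels.)

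**4. Precision.** Let R² be the share of the short model's residual variance that the omitted factors explain. The documents do not give it, so a range is assumed. SE(short)/SE(full) = 1/√(1 − R²). The 95% half-width of the short model is 1.96 × 4.92 × √(2/33) = 2.37 days, for an assumed subgroup of 33 per arm (about a quarter); the full model multiplies this by √(1 − R²).

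| R² | SE ratio | Half-width, short | Half-width, full |
|---|---|---|---|
| 0 | 1.000 | 2.37 | 2.37 |
| 3% | 1.015 | 2.37 | 2.34 |
| 5% | 1.026 | 2.37 | 2.31 |
| 10% | 1.054 | 2.37 | 2.25 |
| 20% | 1.118 | 2.37 | 2.12 |

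**5. Bias and chance imbalance, by simulation.** Assumed: 266 participants; a 25% subgroup; R² shared equally by the five factors; blocks of 4 within strata of sex, puberty status, region and preventive use, with weight unstratified; true effect −1.7; 3,000 trials per row.

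| R² | Mean, short / full | Empirical SE, short / full | Ratio | SD of (short − full) |
|---|---|---|---|---|
| 0 | −1.689 / −1.691 | 1.247 / 1.261 | 0.989 | 0.15 |
| 5% | −1.707 / −1.703 | 1.194 / 1.176 | 1.015 | 0.29 |
| 10% | −1.702 / −1.705 | 1.213 / 1.174 | 1.033 | 0.38 |
| 20% | −1.738 / −1.715 | 1.202 / 1.093 | 1.100 | 0.51 |

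Both models centre on −1.7 within Monte Carlo error (about 1.2/√3000 = 0.02). The ratios fall a little below those in step 4 because the simulation includes the cost of estimating five extra terms. The last column shows how far the two estimates drift apart within one trial: at R² of 5%, 10% and 20% this is 0.29/1.7 = 17%, 0.38/1.7 = 22% and 0.51/1.7 = 30% of the planning effect.

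**6. Two models for one result.** Section 6.2.4 analyses headache days of at least moderate severity by age (6–11, 12–17) with the short model. Section 6.3.2 asks for each secondary endpoint's specified method in the same two age groups. For this endpoint that method is the ANCOVA with all five factors and as-randomised strata values.

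**The case against.** The case for leaving the section alone is fair in several respects. The short model is prespecified with worked examples, the analysis is exploratory, and it sits outside the section 7 testing hierarchy, so no error rate is affected. The protocol (9.2.4.2) leaves subgroup details to the SAP. Randomisation is stratified by sex, puberty status, preventive use and, through country, region, which limits imbalance in four of the five factors. Imbalance in the subgroup factor itself cannot distort its own model. Section 6.3.2 already gives covariate-adjusted results by age for the secondary endpoints. All of this stands, and it keeps the point small.

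It does not remove the point. Stratification protects less within a subgroup: the nine countries in SAP Table 1 × 2 × 2 × 2 make 72 cells for 278 participants, about 4 each, and weight category is not stratified at all. The 6.3.2 analyses do not cover migraine days as a continuous endpoint, and for headache days they create the duplication.

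A reader might infer that the forest-plot estimates are biased or cannot be compared with the primary result. The documents do not support that: a mean difference from a linear model is collapsible, so both models target the same effect on the same scale, and the simulation shows no bias. A reader might also infer that every subgroup model drops all five factors; only age and race do. Nor is a loss of precision established, because it depends on prognostic strength that the documents do not report.

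**Conclusion.** The omission is real and unexplained, and it departs from the SAP's practice in its other ANCOVA and MMRM analyses. Its consequence is modest. The subgroup estimates are unbiased but not identically adjusted to the primary estimate, and they leave out factors used to stratify randomisation. If the factors are prognostic, standard errors are about 1.5%, 2.6% or 5.4% larger at an assumed R² of 3%, 5% or 10%; at zero there is no gain, and the simulation shows about a 1% loss. These sizes rest on the assumed R², subgroup share, factor coding and block size, and on 4.92 as the residual SD of the short model. The clash between 6.2.4 and 6.3.2 needs no such assumption. This is a free improvement of low severity that touches neither the primary result nor the testing sequence.

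**What to change.** - Fit each subgroup ANCOVA as the 6.2.3.3 model (all primary covariates, actual values, the endpoint's own baseline) plus the subgroup main effect where not already present and treatment-by-subgroup. Use the same covariates in the by-month MMRM. If the sponsor prefers the short model, state why.
- Use this one model for headache days of at least moderate severity by age in both 6.2.4 and 6.3.2.
- Show on the forest plot an overall estimate from the matching model.

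The cost is a change to the model statement and four or five degrees of freedom out of about 260. The note to file appended to the SAP says that the trial analysis was conducted. If the subgroup models have been run, keep the prespecified results and report the fuller models as added analyses in the CSR appendices, as SAP 2.5.2 provides for exploratory analyses outside the SAP.

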6.3. Secondary Efficacy Endpoints and Analysis

The secondary efficacy endpoints are as follows:

- mean change from baseline (28-day baseline period) in monthly average number of headache days of at least moderate severity during the 12-week period after the first dose of IMP
- proportion of participants reaching at least 50% reduction in the monthly average number of migraine days during the 12-week period after the first dose of IMP
- mean change from baseline (28-day baseline period) in the monthly average number of days of use of any acute headache medications during the 12-week period after the first dose of IMP
- mean change from baseline (day 1) in migraine-related disability score, as measured by the Pediatric Migraine Disability Assessment (PedMIDAS) questionnaire, at 12 weeks after administration of the first dose of IMP
- mean change from baseline (day 1) in quality of life, as measured by the Pediatric Quality of Life Inventory (PedsQL), at 12 weeks after administration of the first dose of IMP
- proportion of participants developing ADAs throughout the trial. The impact of ADAs on safety and efficacy will be analyzed if the number of ADA-positive participants allows.

6.3.1. Definition

6.3.1.1. Electronic Headache Diary Data

The change from baseline in the monthly average number of days of secondary efficacy variables (eg, migraine days, headache days of at least moderate severity, days of use of any acute headache medications etc.) **during the 12-week period** after the 1st dose of IMP will be derived

similar to the primary variables using the e-diary data collected through the corresponding headache diary questions ([Appendix A](#)). The baseline values and the postbaseline values will be calculated using formula [\(3\)](#) and [\(1\)](#) respectively. ***The change*** is calculated as ***postbaseline value – baseline value***.

The percent reduction in the monthly average number of migraine days ***during the 12-week period*** after the 1st dose of IMP will be calculated by formula [\(4\)](#) in Section [6.1](#). The participant is considered as a responder if the percent reduction is 50% or more. If a participant is early discontinued from the trial, he/she will be counted as a non-responder.

6.3.1.2. Migraine Disability Assessment (PedMIDAS)

The PedMIDAS questionnaire is a 6-item instrument developed to assess headache-related disability which can be self-administered by the participant or administered by a caregiver. It has been validated in participants aged 4 through 18 years and includes questions related to the impact of headache on school performance, disability at home (eg, inability to do chores or homework), and social/sport functioning. The PedMIDAS questionnaire is completed at baseline (visit 2) and the EOT visit (visit 5). The total score, ie, the sum of the 1st 6 questions, is used for grading of disability, with scores of 0 to 10, 11 to 30, 31 to 50, and >50 interpreted as disability grades 1 (little or no disability), 2 (mild disability), 3 (moderate disability), and 4 (severe disability), respectively.

6.3.1.3. Migraine-Specific Quality of Life

The Pediatric Quality of Life Inventory (PedsQL) 4.0 is a brief 23-item health-related quality of life instrument that evaluates quality of life in 4 areas of functioning: physical, emotional, social, and school functioning. The PedsQL 4.0 has 4 age ranges: toddlers (2 through 4 years), young child (5 through 7 years), child (8 through 12 years), and adolescent (13 through 18 years). This trial will use the young child, child, and adolescent formats. The PedsQL 4.0 asks respondents to indicate how much of a problem each item has been during the past month. For the child and adolescent self-report (8 through 18 years of age) and the parent report forms, respondents use a 5-point Likert scale to rate the item severity (0=never a problem; 1=almost never a problem; 2=sometimes a problem; 3=often a problem; 4=almost always a problem). For younger children (5 through 7 years of age), a simplified 3-point Likert scale, anchored with a happy and a sad face, is used (0=not at all a problem; 2=sometimes a problem; 4=a lot of a problem) to increase further the developmental sensitivity of the measure. The PedsQL 4.0 yields a total quality of life score and 2 summary scores: Physical Health Summary Score and Psychosocial Health Summary Score. To obtain scores, items are reverse scored, transformed to a 0 through 100 scale (0=100, 1=75, 2=50, 3=25, 4=0), and averaged; total scores near 0 indicate lower quality of life, while scores approaching 100 indicate higher quality of life. The PedsQL version that will be used for the participant for the duration of the trial will be based on the age of the participant at visit 2 and will not change during the course of the trial.

6.3.2. Analysis

An ANCOVA method, which is similar to the primary analysis setup, will be used for the analysis of the mean change from baseline in the monthly average number of days of secondary efficacy variables ***during the 12-week period*** derived from headache diary data. The model will include treatment, sex, puberty status, region, weight category (<45.0 kg or \geq 45.0 kg), and

baseline preventive migraine medication use (yes/no) as fixed effects and the baseline values as a covariate. The stratification factors (as randomized) will be used in the model. The LS means for the treatment groups, LS means and 95% confidence intervals for the treatment differences (TEV-48125 – placebo), and associated p-values will be provided.

Participants not receiving concomitant preventive medication constitute the sub-population who don't take any preventive migraine medications listed in the protocol, ie, with baseline preventive migraine medication use = no.

If a participant has less than 10 days of e-diary data entries after the 1st dose of IMP, the missing data handling method for the primary variable discussed in Section 4.3 will be applied for the monthly average number of days of secondary efficacy variables *during the 12-week period*.

Similar to the sensitivity analysis for the primary efficacy variable described in Section 6.2.3.1 an MMRM model will be implemented to estimate the mean change from baseline for the following endpoint by month and for overall 3 months after the 1st dose of IMP.

- mean change from baseline (28-day run-in period) in the monthly average number of days of use of any acute headache medications

LS means for the treatment groups, LS means and corresponding 95% confidence intervals for the treatment differences (TEV-48125 – placebo), and associated p-values will be calculated by month and for the overall treatment period.

The LS means \pm SE of e-diary efficacy variables estimated by MMRM will be plotted by month for each treatment group.

For the proportion of responders, defined as at least 50% reduction from baseline in the monthly average number of migraine days, a logistic regression model will be used with the following factors: treatment, sex, region, puberty status, weight category (<45.0 kg or ≥ 45.0 kg), preventive medication use at baseline (yes/no) and baseline number of migraine days. The stratification factors (as randomized) will be used in the model. The odds ratio, 95% confidence interval for the odds ratio, difference from placebo and p-value for the treatment comparison will be presented.

The change from baseline values in the PedMIDAS total score and in the PedsQL psychosocial health summary score, physical health summary score and total scores will be analyzed using the same ANCOVA method as described above.

The proportion of participants positive for ADAs throughout the trial will be summarized.

For each of the secondary endpoints, the specified method of summary/analysis will also be performed for the following subgroups:

- participants by age group (6-11 years, 12-17 years)

6.4. Other Efficacy Endpoints

6.4.1. Definition

6.4.1.1. Electronic Headache Diary Data

For the purpose of this trial, a headache day of at least moderate severity will be defined as a calendar day (00:00 to 23:59) where the participant reports either of the following:

[figure not shown]
- headache pain that lasts ≥ 2 hours with a peak severity of at least moderate severity
- the participant used acute headache medication (NSAIDs, paracetamol, triptans or ergots) to treat a headache of any severity or duration

The derivation logic is presented in [Appendix B](#).

The percent reduction in the monthly average number of migraine days during the 12-week period after the 1st dose of IMP will be calculated by formula (4) in Section 6.1. The participant is considered as a responder reaching 50%, 75% or 100% reduction if his/her percent reduction is 50% or more, 75% or more, or 100% respectively. Similar definition will be applied to calculate the proportion of participants reaching at least 50%, 75% or 100% reduction in the monthly average number of headache days of at least moderate severity during the 12-week period after the 1st dose of IMP. If a participant is discontinued early from the trial, he/she will be counted as a non-responder.

The percent reduction in the monthly number of migraine days during the 4-week period after each dose for months 1, 2, and 3 will be calculated by formula (4) where the postbaseline value will be the number of headache days of at least moderate severity prorated to 28 days for month 1, month 2, and month 3, respectively. If the participant has 50% reduction or more in month 1, he/she will be considered responder during the 4-week period after 1st dose of IMP. In addition, if the participant also has 50% reduction or more in month 2 and 3, he/she is a responder for months 2 and 3, and the level of effect is sustained throughout the 12-week period after the 1st dose of IMP for this participant. Similar definition will be applied to calculate the proportion of sustained responders reaching at least 75% reduction. The proportion of sustained responders reaching at least 50% and 75% reduction in the number of headache days of at least moderate severity will be derived similarly.

The headache day of any severity will be defined as a calendar day (00:00 to 23:59) with headache pain that lasts ≥ 2 hours of any severity or a day when the participant used acute headache medication (triptans, ergots, NSAIDs or paracetamol) to treat a headache of any severity or duration.

The change from baseline (run-in period) in the number of headache days of at least moderate severity days ***during the 4-week period*** after the 1st dose of IMP will be derived similar to the primary endpoint using only the 1st month diary data.

6.4.1.2. [REDACTED]

[REDACTED]

[REDACTED]

[REDACTED]

[REDACTED]

